**Table 7      Expected distance between observed proportion and confidence limit (Clopper-Pearson 95% CI width)**

Proportion of Patients with Total OCS Reduction	Sample Size			
	100	150	300	600
50	±10.2	±8.3	±5.8	±4.1
60	-10.3, +9.7	-8.3, +7.9	-5.8, +5.6	-4.0, +4.0
70	-10.0, +8.8	-8.0, +7.2	-5.5, +5.1	-3.8, +3.6
80	-9.2, +7.3	-7.3, +6.1	-5.0, +4.4	-3.4, +3.1

The table also shows that the 95% Cis for subpopulation analyses as small as 100 are ≤10% from the point estimate for proportions between 70% and 80% and 10.2% for a proportion of 50%.

A sample size of 300 patients is expected to provide 95% Cis for a single proportion extending approximately 5.8% from the point estimate of a 50% success rate.

### **8.3      Definitions of analysis sets**

The following statistical analysis sets will be defined to support data analyses of the study.

#### **8.3.1    All patients analysis set**

This analysis set comprises all patients screened for the study and will be used for reporting of disposition and screening failures.

#### **8.3.2    Full analysis set**

All enrolled patients who received at least one dose of benralizumab will be included in the FAS, irrespective of their protocol adherence and continued participation in the study. Patients will be analyzed irrespective of whether they prematurely discontinue, according to the intent-to-treat principle. Patients who withdraw from the study will be included up to the date of their study termination.

All efficacy analyses will be performed using the FAS. For consistency, demographic and baseline characteristics will be presented using the FAS.

### **8.3.3 Safety analysis set**

The FAS will be used for all safety analyses.

Analysis sets for the PONENTE Long Term Follow Up substudy will be detailed in Appendix [K](#).

## **8.4 Outcome measures for analyses**

The following study outcome measures are designed to support primary, secondary, and exploratory objectives of the study.

For a response outcome, if a patient withdraws from the study before reaching the defined endpoint, the patient will be considered as non-successful.

For a time-to-event outcome, if a patient withdraws from the study before reaching the defined endpoint or does not reach the endpoint by the end of the predefined study phase, the patient will be censored at the withdrawal date or at the end date of the corresponding study phase, whichever is earlier.

For outcomes measured in continuous data such as cumulative dose, ACQ-6 score, and SGRQ score, no imputation will be performed for missing outcomes.

### **Primary efficacy outcome variables**

- Patients who achieve 100% reduction in daily OCS dose that is sustained over at least 4 weeks without worsening of asthma (as defined in Section [5.1.2.1](#) of the protocol)
- Patients who achieve 100% reduction or daily OCS doses of  $\leq 5$  mg, if reason for no further OCS reduction is AI, that are sustained over at least 4 weeks without worsening of asthma

### **Key supportive outcome variables**

- Patients who achieve a daily OCS dose of  $\leq 5$  mg that is sustained over at least 4 weeks without worsening of asthma
- Patients who achieve a  $\geq 90\%$ ,  $\geq 75\%$ , and  $\geq 50\%$  reduction in daily OCS dose, sustained over at least 4 weeks without worsening of asthma
- Change from baseline in daily OCS dose (mg) from start of OCS reduction to end of the OCS reduction phase

### **Secondary efficacy outcome variables**

- Change in daily OCS dose from the end of OCS reduction phase to the end of the maintenance phase (at EOT visit)
- Time to first increase in OCS dose during the maintenance phase, after achieving the minimum OCS dose during the OCS reduction phase

- ACQ-6 scores at baseline (Visit 2), Visit 3, initial morning cortisol test, end of OCS reduction phase, and monthly from end of OCS reduction phase to end of maintenance phase (EOT visit)
- Change from baseline in ACQ-6 score to Visit 3, end of OCS reduction phase, and end of maintenance phase (EOT visit)
- Responder analysis of ACQ-6 scores from Visit 2 through end of maintenance phase
- Change from baseline (Visit 2) in SGRQ total scores to the end of maintenance phase (EOT visit)
- Responder analysis of SGRQ total scores at the end of maintenance phase

#### **Safety outcome variables**

- Patients with complete AI
- Annualized asthma exacerbation rate
- Annualized asthma exacerbation rate leading to hospitalization or emergency room visit
- AEs
- SAEs
- GTI

#### **Exploratory outcome variables**

- Change from baseline (Visit 1) blood eosinophils
- PGIC at Weeks 1, 2, 3, and 4

Outcome variables for the PONENTE Long Term Follow Up substudy will be detailed in Appendix [K](#).

## **8.5 Methods for statistical analyses**

Statistical tabulation will be presented for overall patients and by baseline OCS dose level, category of baseline eosinophil count, and category of duration of chronic OCS use.

Continuous variables will be summarized using the mean, two-sided 95% CI of the mean, the standard deviation, median, minimum value, and maximum value. Categorical variables will be summarized using frequency counts and percentages, as well as a two-sided 95% CI for proportions computed using exact Clopper-Pearson method. Time to event data will be summarized using median and 25th and 75th percentiles with 95% CIs. Data will be listed in patient-level data listings.

No formal hypothesis will be tested in this study, and no multiplicity adjustment will be applied in the statistical analysis. No imputation will be performed beyond the approach defined for outcome measures in Section 8.4. Imputation for partial date will be detailed in the SAP document.

Analysis methods for the PONENTE Long Term Follow Up substudy will be detailed in Appendix K.

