The purpose of this trial is to assess the potential for reducing the use of maintenance OCS in systemic corticosteroid-dependent asthma patients treated with benralizumab 30 mg (who have severe refractory eosinophilic asthma). This study will allow patients to reduce their OCS dose to 0 mg/day or to the lowest OCS dose that is physiologically possible (given the possibility of AI in this population of patients) and will assess whether a faster OCS down-titration compared with what has been previously studied ([Nair et al 2017](#)) is appropriate. Patients will enter the maintenance phase of approximately 24 to 32 weeks after their OCS dose has been reduced to 0 mg/day (or to the lowest OCS dose possible in case no further OCS down-titration is allowed because of the presence of AI as measured by cortisol levels or in case of inadequate asthma control), which will assess the ability of benralizumab to maintain clinical benefits after OCS withdrawal.

Patients will receive open-label benralizumab 30 mg/mL solution for injection in an accessorized prefilled syringe (APFS). It will be administered subcutaneously (SC) at the study site as every-4-week (Q4W) dosing up until the third dose of benralizumab (Visits 2 to 4) and then every-8-week (Q8W) dosing thereafter. This dose is aligned with the current prescribing information for benralizumab, and an open-label design allows for a real-world assessment of OCS down-titration as it relates specifically to benralizumab effectiveness.

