**Table 2 OCS down-titration approaches**

Initial OCS dose/day	OCS down-titration to reach an OCS dose of:				
	20 mg	10 mg	7.5 mg	5 mg	0 mg
>20 mg	Reduction of 5 mg weekly until reaching dose of 20 mg/day	Reduction of 5 mg Q2W until reaching dose of 10 mg/day	2.5 mg Q2W until reaching dose of 7.5 mg/day	2.5 mg Q4W until reaching dose of 5 mg/day	No AI: reductions of 2.5 mg Q4W until reaching dose of 0 mg/day Risk AI: reductions of 1 mg Q4W and repeat test 2 months later a Complete AI: No OCS dose reduction and repeat test 3 months later b
>10 mg to ≤20 mg		Reduction of 5 mg Q2W until reaching dose of 10 mg/day	2.5 mg Q2W until reaching dose of 7.5 mg/day	2.5 mg Q4W until reaching dose of 5 mg/day	No AI: reductions of 2.5 mg Q4W until reaching dose of 0 mg/day Risk AI: reductions of 1 mg Q4W and repeat test 2 months later a Complete AI: No OCS dose reduction and repeat test 3 months later b
>7.5 mg to ≤10 mg			2.5 mg Q2W until reaching dose of 7.5 mg/day	2.5 mg Q4W until reaching dose of 5 mg/day	No AI: reductions of 2.5 mg Q4W until reaching dose of 0 mg/day Risk AI: reductions of 1 mg Q4W and repeat test 2 months later a Complete AI: No OCS dose reduction and repeat test 3 months later b
>5 mg to ≤7.5 mg				2.5 mg Q4W until reaching dose of 5 mg/day	No AI: reductions of 2.5 mg Q4W until reaching dose of 0 mg/day Risk AI: reductions of 1 mg Q4W and repeat test 2 months later a Complete AI: No OCS dose reduction and repeat test 3 months later b
5 mg					No AI: reductions of 2.5 mg Q4W until reaching dose of 0 mg/day Risk AI: reductions of 1 mg Q4W and repeat test 2 months later a Complete AI: No OCS dose reduction and repeat test 3 months later b

a Risk AI means “partial AI” cortisol testing confirmed with ACTH stimulation testing. After repetition of the test 2 months later, the decision to further reduce OCS dose will be based on the morning cortisol test results. If test results are normal, the OCS dose may be reduced directly to 0 mg/day (if patient is receiving ≤3 mg); the patient will continue receiving 1 mg Q4W if still at risk. If complete AI is indicated, OCS dose will not be modified.

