## 8. STATISTICAL ANALYSES BY ASTRAZENECA

### 8.1 Statistical considerations

The statistical analyses will be fully described in a Statistical Analysis Plan (SAP), as appropriate. Data from the main PONENTE study will be summarized for the population overall and by prespecified subgroups: baseline OCS dose, baseline blood eosinophil count, and duration of chronic OCS. Additional subgroups of interest will be further defined in more detail in the SAP.

Due to the single-arm study design, external data sources may be used to contextualize any change seen in asthma control, asthma exacerbation rate, or other safety endpoints in patients treated with benralizumab following reduction of OCS. Any data sources identified, together with planned analyses, will be described in a separate analysis plan.

Statistical analyses for this study will be conducted using SAS (Cary, NC) version 9.3 or higher and will be performed by AstraZeneca or a designated representative. The data cutoff for the primary analysis will occur when the last patient completes the follow up visit of the PONENTE main study. A separate document (SAP) to address detailed statistical analysis issues for the PONENTE main study will be developed and approved by the time the first patient is enrolled to the study. A second and separate SAP detailing the analyses for the PONENTE Long Term Follow Up substudy will be developed and approved prior to the final database lock (DBL) of the main study.

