#### **8.5.4 Subgroup analysis**

Prespecified subpopulations will include the following:

- Patients with baseline OCS dose  $>10$  mg/day,  $>5$  mg/day to  $\leq 10$  mg/day, and  $5$  mg/day
- Patients with baseline blood eosinophil count:
  - $<150/\mu\text{L}$  and  $\geq 150/\mu\text{L}$ ;
  - $<300/\mu\text{L}$  and  $\geq 300/\mu\text{L}$ ; and
  - $<150, \geq 150$  to  $<300$ , and  $\geq 300$  cells/ $\mu\text{L}$
- Patients with duration of chronic OCS use  $<1$  year and  $\geq 1$  year

Additional subgroups may be described in the SAP.

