4.1 General principles

The data analyses will be conducted using the SAS® System version 9.3 or above (SAS Institute Inc., Cary, NC). All SAS® programs used to generate analytical results will be developed and validated according to AstraZeneca SAS® programming standards.

For safety analyses, the statistical tabulation will be presented for all patients in the full analysis set (FAS). For demographics and patient characteristics and efficacy analyses, the

statistical tabulation will be presented for all patients in the FAS and for the following subpopulations:

- Patients with baseline OCS dose >10 mg/day, >5 mg/day to ≤10 mg/day, and 5 mg/day
- Patients with baseline blood eosinophil count:
 - <150/μL and ≥150/μL;
 - <300/μL and ≥300/μL;
 - <150, ≥150 to <300, and ≥300 cells/μL
- Patients with duration of chronic OCS use <1 year and ≥1 year.

For summary statistics for absolute and percentage OCS dose reduction from baseline to the end of the OCS reduction phase, the statistical tabulation will also be presented for the following subgroups:

- Patient's AI status at the end of the OCS reduction phase*:
 - Normal;
 - Partial AI;
 - Complete AI.

* Note that AI status at the end of the OCS reduction phase will be determined by the status at the repeat morning cortisol test (± ACTH stimulation test) for those with partial or complete AI at the initial morning cortisol test (± ACTH stimulation test) and by the status at the initial morning cortisol test (± ACTH stimulation test) for those with normal cortisol levels at the initial morning cortisol test (± ACTH stimulation test). Results from additional testing at the end of the OCS reduction phase for those with partial AI (see section 1.2) will not be included.

For summary statistics for absolute change in OCS dose from the end of the OCS reduction phase to the end of the maintenance phase, the statistical tabulation will also be presented for the following subgroups:

- Patient's AI status at the end of the maintenance phase:
 - Normal;
 - Partial AI;
 - Complete AI.

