4.2.7 Safety outcome variables

All safety variables will be summarised using the full analysis set (FAS) and data presented as a single group.

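### Apart from adrenal status, the SAP drops the protocol's tabulation of safety by baseline OCS dose, exacerbation rates included, and does not declare the change

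*Protocol*

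**What the plan says.** Protocol 8.5, which governs all the analysis subsections beneath it, says: "Statistical tabulation will be presented for overall patients and by baseline OCS dose level, category of baseline eosinophil count"; duration of chronic OCS use is the third factor. Protocol 8.1 says: "Data from the main PONENTE study will be summarized for the population overall and by prespecified subgroups: baseline OCS dose", followed by the other two factors. Neither sentence excludes safety.

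Protocol 8.5.3 (safety outcomes) names a split by baseline OCS dose for AI. It describes the annualised exacerbation rate, adverse events and the glucocorticoid toxicity index without naming one.

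SAP 4.1 gives subpopulation tables to demographics, patient characteristics and efficacy, and puts safety on the full analysis set. SAP 4.2.7 says: "All safety variables will be summarised using the full analysis set (FAS) and data presented as a single group". SAP 4.2.7.4 summarises exacerbations by three study periods and by nothing else. SAP 4.2.7.1, however, repeats the AI results by baseline OCS dose and by duration of OCS use.

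SAP Section 6 lists three changes from the protocol: two added sensitivity analyses, and ANCOVA in place of a repeated-measures model for ACQ-6. Safety subgroups are not among them.

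**The concern.** Protocol 1.3 names exacerbation or worsening on OCS withdrawal as a risk, and Protocol 2.3 makes the annualised exacerbation rate a key safety outcome. How fast and how far a patient is tapered depends on starting dose (Protocol Table 2). A reader will therefore want to know whether exacerbations during tapering differ between patients starting at 5 mg/day and those starting above 10 mg/day. The protocol promises that table. The SAP removes it without comment, and a single overall rate cannot answer the question.

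**Working it through.** **1. The two documents side by side**

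| Output | Protocol | SAP |
|---|---|---|
| Primary endpoints | Split by dose in the synopsis and under the general rule of 8.1/8.5; 8.5.1 itself names none | By dose (4.2.5) |
| ACQ-6 change, time to first OCS increase | General rule only; 8.5.2 uses dose as a covariate and names no split | By dose (4.2.5) |
| AI status | General rule, plus an explicit split in 8.5.3 | By dose and duration (4.2.7.1) |
| Exacerbation counts and rates | General rule; 8.5.3 names no split | Overall only, by study period (3.3.2, 4.2.7.4) |
| Adverse events, laboratory data, vital signs, toxicity index | General rule | Overall only |

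The SAP thus applies the general rule to secondary efficacy outcomes whose own protocol subsections name no split, but not to exacerbations, whose subsection is equally silent.

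**2. Do other planned outputs fill the gap?**
- Time to first OCS increase is repeated by dose group, but counts events in the maintenance phase only (SAP 3.2.2).
- SAP 4.2.5.1 compares baseline dose between patients stopped by two or more exacerbations and patients who reached 0 mg. It conditions on the outcome and gives no rate.
- The primary endpoints register a second exacerbation, because it ends tapering. After a first one the patient may resume the taper and still succeed.
- Exacerbations and non-achievers are listed by patient. A listing is not a rate.

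**3. Starting dose sets the schedule**

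Initial speeds from Table 2 are:
- above 20 mg ("Reduction of 5 mg weekly until reaching dose of 20 mg/day"): 5/1 = 5 mg per week
- >10 to ≤20 mg: 5/2 = 2.5 mg per week
- >7.5 to ≤10 mg: 2.5/2 = 1.25 mg per week
- >5 to ≤7.5 mg, and 5 mg without AI: 2.5/4 = 0.625 mg per week

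With the first cut at Week 4 and no AI or exacerbation, 0 mg is reached at week 8 from 5 mg, week 16 from 10 mg, week 20 from 20 mg and week 25 from 40 mg. Check against the synopsis durations, adding the 24-week minimum maintenance phase: 8 + 24 = 32 weeks (stated about 32) and 25 + 24 = 49 weeks (stated about 48).

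SAP 3.3.2 divides total exacerbations by total follow-up. From first dose to 0 mg, a 40 mg starter therefore carries 25/8 = 3.1 times the weight of a 5 mg starter in the single figure.

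**4. What one pooled rate can hide**

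If one group supplies a share f of follow-up and has R times the rate of the rest, then pooled/rest = 1 + f(R − 1). The documents give neither f nor R, so these values are assumptions:
- f = 0.1, R = 1.5: 1.05
- f = 0.2, R = 2: 1.2
- f = 0.3, R = 2: 1.3
- f = 0.3, R = 3: 1.6

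**5. Precision**

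Protocol Table 7 gives ±4.1 points at 50% for n = 600 and ±10.2 for n = 100. Exact Clopper-Pearson limits reproduce both. One other cell, the upper distance at 60% and n = 600, computes to +3.9 against a printed +4.0, which is immaterial.

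For exacerbation rates, assume 0.9 years of follow-up each and 0.5 events per year. A group of 120 gives 108 patient-years, 54 events and an exact Poisson 95% interval of 0.38 to 0.65. A group of 60 gives 54 patient-years, 27 events and 0.33 to 0.73. Overdispersion would widen both, and the shorter reduction period would be less precise.

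For success proportions in a possible row above 20 mg/day, at 50%: ±24.0 points for n = 18, ±18.7 for n = 30 and ±13.2 for n = 60 (an assumed 3%, 5% and 10% of 600).

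**The case against.** The best defence is that the specific section governs. Protocol 8.5.3 names a dose split for AI alone, which would be redundant if the general sentence already covered safety; the synopsis attaches the subgroups to the primary outcomes; and the SAP follows this pattern. That makes the omission understandable, but does not clear it. Protocol 8.5.1 and 8.5.2 name no dose tables either, yet the SAP produces them under the general rule. Nor does this defence explain why SAP 4.2.7 contradicts 4.2.7.1.

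It is also fair that exacerbation harm is not invisible by dose. It enters the primary endpoints through the two-event stopping rule, and ACQ-6 deterioration is tabulated by dose group. The missing item is the rate during reduction, not all trace of the harm.

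A reader might go further and infer that pooling everyone above 10 mg/day defeats the trial's aim on taper speed. The documents do not support this:
- The >10 mg/day cut is the protocol's own (8.5.4), so it is not a SAP departure.
- Protocol 1.2 says the trial "will assess whether a faster OCS down-titration compared with what has been previously studied", meaning the whole schedule against the earlier trial, not weekly against two-weekly steps within this one.
- Weekly steps last only until 20 mg/day (weeks 4 to 7 from 40 mg). Below that the Table 2 schedule is the same for both strata.
- Speed also varies within strata, through the slower taper of Table 3 after an exacerbation and the 1 mg steps below 5 mg, so dose strata are not the only internal evidence on it.

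**Conclusion.** The concern holds in a limited form. Read as written, Protocol 8.1 and 8.5 promise safety tables by baseline OCS dose; the SAP delivers them for AI status only, contradicts itself on that exception, and does not declare the rest. The consequence is one missing descriptive result that matters: exacerbation rates during OCS reduction by starting dose. It would be wrong to say that all safety is shown as one group, or that high-dose exacerbations would be lost altogether.

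The primary estimates and their intervals are unaffected. How much the single rate could mislead is unknown: the illustrative 1.05 to 1.6 rests on assumed shares and rate ratios. Dose-group rates would be descriptive, because starting dose is tied to both disease severity and schedule.

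**What to change.** - In SAP 4.1, 4.2.7 and 4.2.7.4, tabulate exacerbation counts and annualised rates, including those leading to hospitalisation or an emergency room visit, by the existing groups (5, >5 to ≤10 and >10 mg/day), for the period to the end of OCS reduction and overall. If the first-lock outputs already exist, add the tables at the second lock.
- Reword SAP 4.2.7 so that it allows the AI tables in 4.2.7.1.
- In SAP Section 6, list every safety variable that will still be shown only overall, or without the eosinophil or OCS-duration split.
- Optional and descriptive only: add a row above 20 mg/day, with its n and exact interval, because the >10 mg/day group pools weekly with two-weekly starters. Protocol 8.5.4 lets the SAP add subgroups. The row may be small and cannot separate taper speed from starting dose.

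Cost: a few lines of SAP text and repeat runs of planned tables on data already collected, using dose groups already derived for efficacy. The drawback is wide intervals in any small group.

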### **8.5.1 Analysis of the primary variables**

The count and proportion (with 95% CI) of patients who achieve 100% reduction in their OCS dose, sustained for at least 4 weeks without worsening of asthma or resumed OCS treatment, and the count and proportion of patients who achieve 100% reduction or a daily OCS dose of  $\leq 5$  mg, if reason for no further OCS reduction is AI, sustained over at least 4 weeks without worsening of asthma, will be tabulated.

The same analysis will be carried out for the supporting endpoints: patients who reduce to a daily OCS dose of  $\leq 5$  mg sustained over at least 4 weeks without worsening of asthma; and patients who achieve a  $\geq 90\%$ ,  $\geq 75\%$  and  $\geq 50\%$  reduction in their daily OCS dose without worsening of asthma.

All 95% Cis for proportions will be calculated using the Clopper-Pearson exact method.

For patients who do not achieve 100% reduction in their daily OCS dose, the reason for no further reduction will be listed.

Change from baseline in OCS dose variables will be summarized using descriptive statistics in tables and graphs (supporting primary and secondary endpoints).

### **8.5.2 Analysis of the secondary variables**

#### **8.5.2.1 Time to 1st OCS increase**

Time to first OCS increase in the maintenance phase will be summarized using median, 25th and 75th percentiles (with 95% Cis) and Kaplan Meier plots. The start time for the analysis will be the time, in the OCS reduction phase, at which the patient first reaches the minimum stable dose that is continued into the start of the maintenance phase.

Cox-regression model analysis will also be used to summarize and analyze time to first OCS increase; covariates will include at least baseline OCS daily dose and baseline eosinophil count (categorized). If a patient withdraws from the study before reaching the defined endpoint or does not reach the endpoint by the end of the study, whichever is earlier, the patient will be censored at that time point.

